Traditional methods of orbital fractures reconstruction involve intra-operative shaping of orbital implants (titanium mesh). ⁽¹⁰⁾ Orbital fracture reconstruction using selective laser-melting patient-specific implants has been found to be superior to traditional reconstruction methods. ^(8, 11, 12) The challenges with the traditional approach are a significant increase in cost and longer preoperative time (production time). ^(11, 12) There have been no comparisons published between the traditional approach and pre-adjusted patient-specific orbital implants with respect to orbital volume reconstruction.

- Hypothesis #1: Pre-adjusted patient-specific orbital implants will **more accurately restore the orbital volume** to pre-trauma measures than non-patient-specific orbital implants.

Aim #2: To compare postoperative complications.

The main complications due to orbital fractures reconstruction are 1) enophthalmos and 2) diplopia as a result of inadequate orbital volume reconstruction. The incidence of enophthalmos after the traditional orbital reconstruction approach is 7–27%. ^(5, 13, 14) This rate is significantly higher than that observed after using the patient-specific approach (3.7%). ⁽¹²⁾ Again, there are currently no data regarding pre-adjusted, patient-specific orbital floor implants. The incidence of

diplopia after the traditional orbital reconstruction approach is 8–42%,^(14–16) which is significantly higher than that for the patient-specific approach (3.2%).⁽¹²⁾

- **Hypothesis #2:** Pre-adjusted patient-specific orbital implants will **have fewer postoperative complications** than non-patient-specific orbital implants.

Aim #3: To evaluate the length of hospital stay. The typical hospital stay for an orbital floor fracture at Grady Memorial Hospital (GMH) is 1–2 days, depending on the patient's response to surgery.

- **Hypothesis #3:** Pre-adjusted patient-specific orbital implants lead to a **shorter length of stay**, secondary to improved accuracy of implant design, placement, and reduced need for manipulation. This would be expected to lead to decreased postoperative swelling and pain. Orbital fracture reconstruction could be executed as a same-day surgery (outpatient surgery) when utilizing 3DP.

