We expect a **sample size of 60** surgical cases, evenly split between the new treatment and control groups, to have a study powered to **detect at least a 1 cm³ difference in orbital volume** between the groups. The sample size calculation was based on using a two-sample Student's t-test to compare the difference in contralateral orbital volume between the treatment and control groups. We used a **power of 90%**, alpha level of .05, and 1.17 cm³ standard deviation of orbital volume. The 'normal' orbital volume and standard deviation were estimated from the results of Forbes et al. (1984). Sample size calculations were performed with the 'power.t.test' function in R statistical software based on Cohen (1988).⁽²⁵⁾ Taking attrition into account, if 25% of our expected patient enrollment numbers are not met for any reason, **our study would still retain a power of 80%**. Additionally, in the event of attrition from loss-to-follow-up alone, our primary outcomes variable and the bulk of the secondary outcomes variables, including the reduction of orbital volume to less than 2 cm³, operative time, traumatic pupillary mydriasis, orbital compartment syndrome, extra-ocular motility, and plate contour, will be successfully obtained on immediate post-operative hour. **Attrition at these stages will have no effect on the above variables.**

Randomization & Statistical Analysis

Cases will be randomized to the treatment or control arms using a pre-generated block randomization scheme with a **block size of 4** and stratified according to surgeon/specialty. In essence, each surgeon will receive their own list of randomized cases to simplify the logistics of the trial. **The block randomization guarantees that at no point during the trial will there be more than a 3-case difference between the treatment and control arms for each individual surgeon**; thus, it is possible but unlikely that there will be a maximum 9 case difference at some

point (sizes will be equal at completion). The randomization scheme has been pre-generated by a statistician, and the resulting trial arm for each case will be placed in envelopes to be revealed at the time of patient enrollment. The treatment will not be blinded to the physician or the patient; it is not practical to keep knowledge of the procedure concealed.

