The success of the randomization will be evaluated at the start of the analysis by comparing patient characteristics. Differences between the treatment and control arms that do not reach statistical significance using appropriate tests (likely t-tests and chi-square tests) that are smaller than 20% for all characteristics will mean that the groups are ‘balanced’ in our criteria and will be evidence of randomization success. Assuming that standardization is successful, all outcomes will be compared using standard two-sample comparisons. For binary outcomes, such as complications and CT use, Chi-square tests or Fisher’s exact tests will be used depending on the prevalence of the outcome. Two-sample t-tests or Wilcoxon-Mann-Whitney tests (if data are non-parametric) will be used to compare mean orbital volume differences and operative times. Differences in length of stay and costs are likely to be analyzed with two sample t-tests on a log scale (thus, a comparison of geometric means will be made). Finally, logistic regression or other multivariable analyses may be performed to identify risk factors for developing complications or deviations from the normal recovery course.

Statistical Support

Support for statistical analyses will be provided by [name], MSPH, a trained biostatistician, working for the Department of Surgery at Emory University Hospital. All analyses will be conducted or supervised by [name]. [name] has 15 years of experience in data analysis and 7 years of experience working as the department statistician for surgery. He has over 40 peer-reviewed publications to his name and experience with outcomes and health services research as well as basic science research. In the past, he has assisted in the design and analysis of similar trials at Emory University. Regarding the cost-effective analysis, [name] is the primary mentor. He is an experienced researcher and participated in cost-effective research in GMH by comparing the cost effectiveness of 2 types of mandibular fracture treatment. ⁽²⁴⁾

Inclusion & Exclusion Criteria

- The following subjects will be included in the study:
 - 1- Agreed to be enrolled in the study.
 - 2- Indications for surgical repair of orbital floor and/ wall fractures are dependent on several factors:
 - a. Correction or prevention of cosmetic deformity (enophthalmos or inferior dystopia; disruption of greater than 50% of the orbital floor is likely to cause cosmetically apparent enophthalmos.

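### Randomisation is stratified by surgeon/specialty, but no treatment comparison includes surgeon, and the unadjusted tests rest on a baseline-balance check with no analysis stated if it fails

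*Combined protocol and SAP*

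**What the plan says.** All of this is in the section Randomization & Statistical Analysis unless noted.

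- Allocation uses permuted blocks of 4, "stratified according to surgeon/specialty", with a separate list for each surgeon. The plan puts the largest overall imbalance at 3 cases per surgeon and describes it as "possible but unlikely that there will be a maximum 9 case difference". Since 9 / 3 = 3, three strata are implied; Preoperative Assessment also names three specialties.
- At the start of the analysis, patient characteristics are compared between arms "using appropriate tests (likely t-tests and chi-square tests"). Differences that are non-significant and "that are smaller than 20% for all characteristics will mean that the groups are" balanced. The characteristics are not listed, and the plan does not say whether 20% is absolute or relative.
- The next sentence is the condition: "Assuming that standardization is successful, all outcomes will be compared using standard two-sample comparisons". Here standardization can only mean the balance check just described.
- The tests are then named. "For binary outcomes, such as complications and CT use", the plan uses chi-square or Fisher's exact tests. Volume differences and operating times get a t-test or Wilcoxon-Mann-Whitney test. Length of stay and costs get a t-test on the log scale. None includes surgeon.
- The only multivariable analysis is optional and has another purpose: "logistic regression or other multivariable analyses may be performed to identify risk factors for developing complications".

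**The concern.** There are two gaps.

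First, the plan covers only the case in which the check passes. If it fails, nothing says which treatment comparison is reported, so that choice would be made with the data in hand. The check is also a poor gate. Under properly concealed random allocation, baseline differences are due to chance, so a failed check is not evidence that randomisation went wrong.

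Second, stratifying by surgeon removes surgeon differences from the contrast between arms, but the unadjusted test leaves them in its error term. The standard error is then too large whenever surgeons differ in outcome. The trial balances on surgeon and then does not use that balance in the analysis.

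**Working it through.** **1. The plan's own figure.** Inputs from Randomization Sample Size & Calculation: difference 1 cm³, SD 1.17 cm³, alpha 0.05 (two-sided assumed), 30 per arm. The noncentrality is 1 / (1.17 × √(2/30)) = 3.31 on 58 degrees of freedom, which gives power 90.2%. With 45 patients (22 and 23) power is 80.0%. Both stated figures reproduce.

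**2. How often correct randomisation fails the check.** Assumptions: 30 per arm, 20% read as percentage points, independent binary items. The number and prevalence of items are assumed, because the plan gives neither. The per-item failure probability q is found by exact enumeration of two binomial counts, using chi-square, or Fisher's exact test when an expected count is below 5. A list of k items fails with probability 1 − (1 − q)^k. A difference of exactly 20% is possible (6/30), so both treatments of that value are shown.

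| Failure rule | q at 30% to 50% prevalence | 5 items | 10 items |
|---|---|---|---|
| p < 0.05 or difference ≥ 20 points | 0.120 to 0.155 | 47-57% | 72-81% |
| p < 0.05 or difference > 20 points | 0.067 to 0.093 | 29-38% | 50-62% |
| p < 0.05 only | 0.049 to 0.052 | 22-23% | 39-41% |

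For example, 1 − (1 − 0.120)^5 = 0.47. Rare items (5-10% prevalence) fail far less: 1-9% with five items under the strictest rule. If 20% is instead read as relative to the other arm, one binary item reaches it by chance in 46% of trials at 50% prevalence and 64% at 30%.

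**3. Why omitting surgeon is conservative.** With three surgeons, 20 patients each and complete blocks of 4, each surgeon has 10 patients per arm, so surgeon effects cancel in the difference between arms. The true standard error is 1.17 × √(2/30) = 0.302 when 1.17 is the within-surgeon SD. The unadjusted test's pooled variance has expectation 1.17² + (20/29) × σ², where σ is the between-surgeon SD. At σ = 0.6 this is 1.369 + 0.248 = 1.617, an SD of 1.27. The standard error is overstated by about 9% (1.27 / 1.17).

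**4. Size of the loss.** Simulation of three surgeons × 20 in blocks of 4, true difference 1 cm³. The between-surgeon SD is assumed, because the documents give none. Repeat runs agree to within a few tenths of a point.

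Surgeon SD added to 1.17:

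| Surgeon SD (cm³) | Unadjusted power | Adjusted power |
|---|---|---|
| 0 | 90% | 90% |
| 0.27 (5% of total variance) | 89-90% | 90% |
| 0.39 (10%) | 89% | 90% |
| 0.6 | 87% | 90% |
| 0.8 | 84% | 90% |

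The unadjusted type I error is about 3.5% at SD 0.6 and 3% at 0.8; the adjusted test stays at 5%. Unequal strata (36/16/8) give 87.4% against 90.1% at SD 0.6 and 85.0% against 90.2% at 0.8.

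If 1.17 is the total SD, power is about 91.0% unadjusted against 91.5% adjusted at a 5% surgeon share, and 91.8% against 92.9% at 10%.

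**5. Binary outcomes.** Take enophthalmos at 27% against 3.7%, both from Aim #2. The 3.7% is for the patient-specific approach, not the study's pre-adjusted plates, so it is an assumption here. With 10 per arm in each of three strata and no surgeon effect, Mantel-Haenszel and chi-square both have power 0.78; the exact stratified test has 0.61 against 0.59 for Fisher's. Stratifying loses nothing in this case.

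**The case against.** The surgeon half can be called a refinement. No between-surgeon SD is documented, the gain at modest surgeon effects is about half to one and a half points, and if 1.17 is the total SD the unadjusted test keeps its planned power. That stands, and it limits the weight of this half. It does not argue against a change that costs almost nothing when surgeons do not differ.

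The failure rates depend on an unknown list and on how a difference of exactly 20% is treated. That also stands. The robust statement is that chance failure is quite possible, not that any one percentage applies.

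The check uses patient characteristics at the start of the analysis, not outcomes. This narrows the room for an outcome-driven choice but does not close it, because no fallback is named.

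The optional multivariable analysis might include arm and surgeon, and the Treatment charges section refers to a cited cost study's method. The text does not say the first, and the second cannot be checked here. The plan's own analysis section gives only an unadjusted log-scale t-test for costs.

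**Conclusion.** The point holds as a pre-specification gap together with a small, nearly free gain in precision. The missing fail branch and the absence of surgeon from every treatment comparison are plain in the text. How likely the check is to fail depends on the assumed items and on the reading of 20%. The power loss depends on the assumed between-surgeon SD and on whether 1.17 includes it.

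A reader might infer more, and the documents do not support it. The trial is not shown to be underpowered, since both stated power figures reproduce. Ignoring the strata does not inflate false positives; if surgeons differ, it lowers the error rate below 5%. A positive result from the unadjusted test would therefore not be undermined.

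**What to change.** In Randomization & Statistical Analysis, present baseline characteristics by arm descriptively and remove the balance check as a condition for the analysis. Pre-specify, whatever the balance:

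1. A linear model with arm and surgeon/specialty for the primary volume outcome, for operating time, and for length of stay and charges on the log scale the plan already proposes. Where a rank test would be used, use a surgeon-stratified Wilcoxon test.
2. A surgeon-stratified Mantel-Haenszel test for binary complications, or its exact version when events are few.

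Add surgeon/specialty to the table in Data Collection & Analysis. The per-surgeon lists imply that it is known, but the table does not name it.

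The cost is two degrees of freedom in the linear model and one data field. Power stays at about 90% if surgeons do not differ.

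A secondary option is to add pre-operative volume as a covariate. The primary outcome in Study Settings and Patients already requires the measured post-traumatic volume, so this needs no new measurement, only a line in the data table. That section, however, describes the primary outcome both as injured against contralateral volume and as reduction from the post-traumatic volume. The plan must first say which one is modelled.

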- Complex orbital fractures will be exposed and identified via a transconjunctival approach in combination with lateral cantholysis if needed to improve access.
- To record and compare the operative time between the two groups, a stopwatch will be utilized. The time in minutes will be recorded from fracture exposure and identification to final implant placement and fixation.

Postoperative Assessment

During post-operative care, all patients will undergo the following:

- 1) Maxillofacial non-contrast CT scans according to the protocol will be obtained as part of the standard of care in managing orbital fractures.
- 2) The PI will evaluate the orbital volume using OsiriX (medical software). Orbital volume measurements will be obtained to compare the injured and uninjured (contralateral) orbital volumes. OsiriX MD offers advanced processing techniques and has the ability to precisely measure orbital volume. It utilizes the DICOM data from the immediate post-operative CT scans.
- 3) All patients, regardless of the group into which they are randomized, will receive their post-operative assessment by the designated team resident under the supervision of one of the following attendings: [name] for OMFS, [name] for ENT, or [name] for Plastic Surgery.
- 4) All patients, regardless of the group into which they are randomized, will receive their post-operative ocular assessment by [name], ophthalmology attending and Co-PI, or by her fellow [name].

Follow-Up

- All patients will be regularly assessed at 1 week, 3 weeks, and 6 weeks postoperatively.

This is a standard post-operative follow-up schedule for craniomaxillofacial fracture patients. It is also an adequate duration for edema to resolve, which will assist in the accurate evaluation of enophthalmos. The following will be evaluated and recorded by the surgical team at each follow-up visit: enophthalmos, infection, infraorbital nerve injury, traumatic pupillary mydriasis, orbital compartment syndrome, and restricted extra-ocular movement.

- In terms of data collection and data extraction from Epic: PI [name], co-PI [name] and an assigned research coordinator will be involved.

Patient Compensation

All patients enrolled in the study will be compensated with \$100 for their time and to encourage compliance. Their compensation includes the costs of participation in the study (\$50) and the completion of the follow-up visits at week 6.

Data Collection & Analysis

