Data	Time
Age, sex, race, DOB	Pre-operative (pre-op)
Mechanism of injury, time from injury to admission	Pre-op
Type of orbital fracture and other injuries	Pre-op
Indications for surgery	Pre-op
CT scans results (fracture size & location)	Pre-op
Extra-ocular motility indicating which gaze	Pre-op
Level of infraorbital nerve injury	Pre-op
Traumatic pupillary mydriasis	Pre-op
IOP (Intra-ocular pressure)	Pre-op
Enophthalmos (Hertel exophthalmometer measurement)	Pre-op
The use of 3D printed models	Pre-op
The time needed to print the model	Pre-op
Orbital and ocular exam results	Pre-op
Time from admission to surgery	Pre-op
Date of surgery	Pre-op
Length of surgery (minutes)	Operative
Approach	Operative
Intra-operative complications	Operative
Post-operative orbital volume comparison (OsiriX)	Post-operative
Dates of post-operative visits	Post-operative, weeks 1, 3, and 6
Extra-ocular motility indicating which gaze	Post-operative, weeks 1, 3, and 6
Level of infraorbital nerve injury	Post-operative, weeks 1, 3, and 6
Traumatic pupillary mydriasis	Post-operative, weeks 1, 3, and 6
IOP (Intra-ocular pressure)	Post-operative, weeks 1, 3, and 6
Infection	Post-operative, weeks 1, 3, and 6
Enophthalmos (Hertel exophthalmometer measurement)	Weeks 1, 3, and, 6

Overall cost	Post-operative
Need for second surgical procedure	Post-operative, weeks 1, 3, and 6

SIGNIFICANCE AND INNOVATION

This project will test two new and evolving methodologies in the medical world: 1) an office-based 3D printer and 2) pre-adjusted patient-specific implants. These two methodologies have yet to be applied together in orbital fracture reconstruction. Additionally, this study focuses on low-income patients and will be the first of its kind serving this population. Several other benefits include potential savings related to total overall cost, a reduced operative time and postoperative course, and a subsequent increase in both the quality of care and the value of care, especially in the underserved patient population cared for at GMH. We expect the results of this study to be applicable at most major urban trauma centers across the USA and abroad. The results of this study can be used in future studies as a model or pilot study.

FUTURE PLANS

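### Within Aim #2, the only enophthalmos comparison named is yes/no at 2 mm; a week-6 comparison of the Hertel millimetres already scheduled should be pre-specified beside it

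*Combined protocol and SAP*

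**What the plan says.** Specific Aims and Hypothesis, Aim #2, names enophthalmos and diplopia as the main complications. Hypothesis #2 predicts fewer complications with the pre-bent plates. For the control method, "The incidence of enophthalmos after the traditional orbital reconstruction approach is 7–27" per cent. For patient-specific implants the protocol cites 3.7%, and it notes that no data exist for pre-adjusted plates.

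The secondary-outcome definitions under Methodology measure enophthalmos with a Hertel exophthalmometer and call it present when the two orbits differ by more than 2 mm. The table under Data Collection & Analysis lists "Enophthalmos (Hertel exophthalmometer measurement") twice: once pre-operatively, and once at weeks 1, 3 and 6.

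Randomization & Statistical Analysis states "For binary outcomes, such as complications and CT use, Chi-square tests or" Fisher's exact tests, the choice depending on prevalence. It names t-tests or Wilcoxon tests for orbital volume and operative time, and log-scale t-tests for length of stay and cost. It names no analysis of Hertel millimetres, no baseline adjustment, and no visit at which enophthalmos is compared.

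On the 6-week schedule, Follow-Up says "It is also an adequate duration for edema to resolve" and links this to accurate assessment of enophthalmos.

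The sample size is 60 "surgical cases, evenly split between the new treatment and control groups", chosen for orbital volume. No power is given for Aim #2.

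**The concern.** A measured quantity is reduced to a rare event in a small trial. With 30 per arm and 3.7% expected in Group A, the yes/no comparison rests on roughly one Group A event and two to eight control events. A real benefit would often be missed, and a non-significant result on a named hypothesis could be read as no difference. The millimetre readings, including a pre-operative value, will already be on file. If no analysis of them is pre-specified, any later use is post hoc.

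**Working it through.** **1. The plan's own figure.** Inputs are from Randomization Sample Size & Calculation: "detect at least a 1 cm³ difference in orbital volume" and "alpha level of .05, and 1.17 cm³ standard deviation of orbital volume". The effect size is 1/1.17 = 0.855. A two-sided two-sample t-test (sidedness is not stated; two-sided is assumed) needs 29.8, so 30 per arm. Power is 90.2% at 30 per arm and 80.0% at 22.5 per arm (45 cases), which matches "our study would still retain a power of 80" per cent. The stated design reproduces, but it concerns orbital volume only.

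**2. Enophthalmos as yes/no, 30 per arm.** Group A is set at p_A = 3.7%. Control p_C is 7% or 27% (the ends of the protocol's range), with 15% and 20% as points between. Exact power is the sum of Bin(i; 30, p_C) × Bin(j; 30, p_A) over all pairs (i, j) with a two-sided p below 0.05.

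With no event in Group A, Fisher needs six control events:
- 5 against 0 gives 2 × C(30,5)/C(60,5) = 2 × 142,506/5,461,512 = 0.052.
- 6 against 0 gives 2 × 593,775/50,063,860 = 0.024.

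Expected control events are only 30 × 0.07 = 2.1 to 30 × 0.27 = 8.1. Even at 27% the pooled expected count is (8.1 + 1.1)/2 = 4.6 per arm, so the usual rule of five would select Fisher.

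**3. Millimetres, whole distribution shifted.** Assume normal data, equal SD and a one-directional cut at 2 mm. The two rates then imply a standardised shift d = z(1 − p_A) − z(1 − p_C), with z(0.963) = 1.787:
- 7%: 1.787 − 1.476 = 0.311
- 15%: 1.787 − 1.036 = 0.750
- 20%: 1.787 − 0.842 = 0.945
- 27%: 1.787 − 0.613 = 1.174

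Power is from the noncentral t. Adjusting for a pre-operative value with assumed correlation r = 0.5 replaces d by d/√(1 − 0.25).

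**4. Millimetres, a minority of failed repairs.** Let recession be the uninjured minus the operated reading. Assume successes are N(0, SD 1 mm) and failures N(3, SD 0.5 mm), mixed so that the same rates exceed 2 mm. The failure fraction is w = (p − 0.0228)/(0.9772 − 0.0228), which gives 1.5% in Group A and 25.9% in control at 27%. There the mean difference is 3 × (0.259 − 0.015) = 0.73 mm. The average SD is √[(2.53 + 1.12)/2] = 1.35 mm, so d = 0.54 and power is about 54%. The table row is from simulation.

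| Power (%) at control rate | 7% | 15% | 20% | 27% |
|---|---|---|---|---|
| Fisher, exact | 0.6 | 12.5 | 30 | 60 |
| Uncorrected chi-square, exact | 6 | 34 | 55 | 78 |
| t-test in mm, whole shift | 22 | 82 | 95 | 99 |
| Same, with r = 0.5 covariate | 28 | 91 | 99 | >99 |
| t-test in mm, minority of failures | 6–7 | 18 | 32 | 54 |

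Other failure-type parameter sets gave 53% to 62% at 27%.

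**5. Sample size for 80% power, yes/no against mm, whole-shift model.** Per arm: 729 against 164, 104 against 29, 61 against 19, and 37 against 13. The ratios run from 4.4 down to 2.8. They hold only under that model.

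**6. What 30 per arm can detect in mm.** No Hertel SD is given. For assumed SDs of 1, 1.5 and 2 mm, the difference detectable with 80% power is 0.74, 1.10 and 1.47 mm.

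**7. With a 25% shortfall (23 per arm).** Fisher power is about 1% to 52%. The whole-shift t-test has 18% to 97%.

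**The case against.** The strongest objection is that the large gain comes from one model. It needs every patient to move by the same amount, and the documents give no Hertel mean, SD or distribution. If most repairs are near symmetric and a few fail, the millimetre test is about level with Fisher, can fall below it at 27%, and is below the uncorrected chi-square from 15% upward. This stands. The Abstract does cite a linear relation between orbital volume and enophthalmos, which makes a general shift credible, but it does not establish one.

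Second, a mean difference does not answer Hypothesis #2, which concerns fewer complications as the protocol defines them. A signed mean also counts over-projection of the operated eye as benefit. Under the normal model, 3.7% beyond 2 mm puts the Group A mean recession at 2 − 1.79 × SD, which is −0.7 mm at SD 1.5 and −1.6 mm at SD 2. This stands too, and it rules out replacing the defined event.

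Third, the covariate may add little. Surgery aims to correct the pre-operative displacement, edema affects early readings, and r = 0.5 has no source in the documents.

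Fourth, this is a secondary outcome in a trial sized for orbital volume, and Human Subject Protections calls it a pilot. That limits the weight of the point but does not remove it.

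A reader might infer that Aim #2 as a whole discards most of its power. The documents do not support that. Diplopia, infection, nerve injury and the other complications have no Hertel scale. Even for enophthalmos, the loss at 27% under the whole-shift model is from 99% to 60%, and at 7% both analyses are weak. Nor does the plan forbid a millimetre analysis; it simply names none.

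**Conclusion.** The point holds for the enophthalmos comparison alone, as a cheap improvement. That the yes/no test is weak follows from the protocol's own rates and 30 per arm, with the 3.7% borrowed from a different type of patient-specific implant. How much a millimetre analysis would recover depends on an unknown distribution. The two models in the working bracket it between a large gain and none, so it cannot be put as one figure. This supports adding a pre-specified millimetre comparison, and does not support demoting the proportion beyond 2 mm.

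**What to change.** In Randomization & Statistical Analysis:

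- Keep the proportion with a difference above 2 mm as the comparison that answers Hypothesis #2. Name week 6 as the visit and report an exact confidence interval.
- Pre-specify beside it the week-6 operated-minus-uninjured Hertel difference in mm (negative means the operated eye is recessed). Use a linear model with arm, pre-operative Hertel difference and surgeon/specialty stratum, and report the estimate with its 95% confidence interval.
- Report the absolute between-orbit difference at week 6 as well, so that over-projection is not counted as benefit. Its power has not been calculated here.

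The cost is SAP wording and one extra secondary analysis. No new patients, visits or measurements are needed. The downside is one more secondary result to interpret, with a covariate that edema may make uninformative.

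### At 30 per arm, replacing Fisher's exact test with Boschloo's for sparse complications would add about 1 to 12 points of power, with 8 to 12 only at control rates of about 14–27%

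*Combined protocol and SAP*

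**What the plan says.** All references are to the combined protocol and SAP.

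- **Randomization & Statistical Analysis.** For binary outcomes, complications included, "Chi-square tests or Fisher’s exact tests will be used depending on the prevalence of the outcome". No prevalence cut-off, sidedness or significance level is given for these comparisons.
- **Specific Aims and Hypothesis, Aim #2.** Hypothesis 2 is that pre-adjusted implants give fewer complications. "The incidence of enophthalmos after the traditional orbital reconstruction approach is 7–27"%, against 3.7% in a cited study of patient-specific implants. For diplopia the figures are 8–42% and 3.2%. The same section says that no data exist yet for pre-adjusted implants.
- **Randomization Sample Size & Calculation.** The trial has 60 "surgical cases, evenly split between the new treatment and control groups", so 30 per arm. The power calculation concerns orbital volume only: it aims to "detect at least a 1 cm³ difference in orbital volume" with 90% power, "alpha level of .05, and 1.17 cm³ standard deviation of orbital volume". If a quarter of enrolment is missed, "our study would still retain a power of 80"%. No power figure is given for Aim 2.

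**The concern.** With 30 per arm and few events, Fisher's test can take only a few p-values in the relevant range, and none of them lies just under 0.05. Five events against none gives p = 0.052, so the test needs six against none. Part of the permitted 5% error is then unused, and a real difference in complications is more easily reported as no difference. An unconditional exact test can reject some of those borderline tables and still keep the error at or below 5%. Aim 2 has few events to begin with, so power that costs no patients is worth having. The choice must be made in advance: changing the test after seeing a 5 v 0 table would be post hoc.

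**Working it through.** **1. The plan's own figure.** For a two-sided two-sample t-test with difference 1 cm³, SD 1.17 cm³ and alpha .05, the noncentral t gives 29.76, so 30 per arm, with power 90.2% at 30. A 25% shortfall leaves 60 × 0.75 = 45 patients, or 22–23 per arm; power is 79.1% at 22, 80.0% at 22.5 and 80.9% at 23. The stated figures reproduce, which supports reading alpha as two-sided.

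**2. Assumptions for Aim 2.** These are mine, not the plan's: two-sided 5%; Fisher if any expected count is below 5, otherwise uncorrected chi-square; Group A rates of 3.7% (enophthalmos) and 3.2% (diplopia).

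**3. When Fisher applies.** With equal arms, the expected events per arm are half the total, so Fisher is used when fewer than 10 events occur overall. The mean total is 30 × (control rate + Group A rate):
- 15% v 3.7%: 30 × 0.187 = 5.6
- 20% v 3.7%: 30 × 0.237 = 7.1
- 27% v 3.7%: 30 × 0.307 = 9.2
- 42% v 3.2%: 30 × 0.452 = 13.6

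The probability that Fisher is used is about 95%, 84%, 56% and 8% respectively.

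**4. Where the two tests differ.** For 5 v 0, Fisher p = 2 × C(30,5)/C(60,5) = 2 × 142,506/5,461,512 = 0.052. For 6 v 0, p = 2 × 593,775/50,063,860 = 0.024. For 7 v 1, p = 0.052. Boschloo's test uses the Fisher p-value as its statistic. Enumerating all 31 × 31 tables, it can reject for Fisher p up to 0.0692 with maximum size 4.69%; Fisher's own maximum is 2.74%. Within the sparse branch this adds the tables 5 v 0 and 7 v 1, their mirror images with the arms exchanged, and the equivalent tables for events that nearly everyone has. It removes none, so power cannot fall.

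**5. True size**, summing binomial probabilities over the rejection region when both arms share one rate (30 per arm):

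| Common rate | Fisher alone | Plan's mixed rule | Boschloo alone |
|---|---|---|---|
| 5% | 0.15% | 0.15% | 0.7% |
| 10% | 0.94% | 1.2% | 2.3% |
| 15% | 1.7% | 2.9% | 2.9% |
| 20% | 2.2% | 4.2% | 3.1% |

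The maximum size is 5.2% for the mixed rule, with either Fisher or Boschloo in the sparse branch; the chi-square branch sets it.

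**6. Power.** The gain is the probability of the added tables. For 20% v 3.7%, with control events first:
- P(5 v 0) = 0.1723 × 0.3227 = 0.0556
- P(7 v 1) = 0.1538 × 0.3719 = 0.0572
- Sum = 0.1128, or 11.3 points; the other added tables are negligible here.

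| Control v Group A | Plan's rule | Boschloo in sparse branch | Gain (points) | Gain at 22 per arm |
|---|---|---|---|---|
| 7% v 3.7% | 0.6% | 2.0% | +1.4 | +0.1 |
| 10% v 3.7% | 2.8% | 6.8% | +4.0 | +0.5 |
| 15% v 3.7% | 13.5% | 22.5% | +9.1 | +2.3 |
| 20% v 3.7% | 32.8% | 44.1% | +11.3 | +5.0 |
| 27% v 3.7% | 64.0% | 72.2% | +8.2 | +6.9 |
| 8% v 3.2% | 1.2% | 3.7% | +2.4 | +0.2 |
| 20% v 3.2% | 35.2% | 47.4% | +12.2 | +4.8 |
| 30% v 3.2% | 77.2% | 83.5% | +6.3 | +6.4 |
| 42% v 3.2% | 97.3% | 98.1% | +0.7 | +2.4 |

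Gains are taken before rounding. At 22 per arm Fisher already rejects 5 v 0 (p = 0.048), so the gain is smaller at most of these rates.

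**7. Scale of the underlying problem.** The pooled-variance normal formula, n = [1.96√(2p̄q̄) + 0.8416√(p₁q₁ + p₂q₂)]²/(p₁ − p₂)², gives for 80% power at 7% v 3.7%: (0.6238 + 0.2671)²/0.033² = 729 per arm. At 27% v 3.7% it gives (0.9992 + 0.4060)²/0.233² = 37 per arm.

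**The case against.** The strongest reply is that Fisher's test is valid, familiar and protects the error rate. These are secondary outcomes with no power claim, and several complications are tested without multiplicity control, so a conservative test is defensible. The real limit on Aim 2 is sample size. Most of this stands, and it is why the point is an efficiency gain and not a correction. It does not remove the point: Boschloo's test also holds the error at or below 5%. Fisher's conservatism is also a poor substitute for multiplicity control, because its amount depends on the event rate and nobody has chosen it.

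A reader might go further than the documents allow in four ways.
- **That low-prevalence outcomes lose 8–12 points.** At 7–10% control rates the gain is about 1–4 points, and power stays below 8% with either test.
- **That the plan wastes more than half of its error allowance.** That fits Fisher alone up to common rates of about 20%. The plan also allows chi-square, and under the mixed rule size is already 2.9% at 15% and 4.2% at 20%.
- **That the replacement restores 5%.** Boschloo's size is 0.7% at a 5% event rate.
- **That the plan expects 3–4% events in Group A.** It cites those rates for a different implant type.

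The diplopia rows also carry less weight, because diplopia is not a named item in the secondary outcome list, the follow-up list or the post-operative rows of the data table.

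**Conclusion.** The concern holds as a modest efficiency point on a secondary aim. At 30 per arm, Boschloo's test in the sparse branch is never less powerful than Fisher's. Its benefit is greatest in the middle of the enophthalmos range: at 17%, the midpoint of 7–27%, power against 3.7% rises from 20.4% to 30.8%. At the ends of the documents' ranges the benefit is small, and under the plan's own 25% shortfall it does not exceed about 7 points at the rates tried. No choice of test rescues Aim 2 at low control rates.

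These figures rest on a two-sided 5% level, an expected-count cut-off of 5 and Group A rates borrowed from cited patient-specific implants. The plan states none of the three for complications.

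**What to change.** In Randomization & Statistical Analysis, before any results are seen:

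1. Name Boschloo's unconditional exact test, two-sided 5%, in place of Fisher's for sparse binary outcomes.
2. State the cut-off, for example any expected count below 5, and keep the uncorrected chi-square test otherwise.
3. Report the risk difference with its confidence interval for each complication, so that a non-significant result at these event counts is not read as evidence of no difference.

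The cost is a sentence or two of text and free software (R or Python), with no added patients or data. The downside is that clinical readers know the test less well, so the report should explain it in a line.
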